Because randomization to study arm will be at the bar level, we will use analytic techniques (generalized linear mixed models [GLMMs] and multilevel structural equation models [MSEMs]) that account for clustering of individuals nested within bars and repeated measures within individuals and allow for participant-level missing data [18,19,20]. Selection of model link functions (e.g., identity, log, logit) and error distributions (e.g., normal, Poisson, binomial) in GLMMs and MSEMs will be guided by the scale of measurement and observed distribution of the outcome measure. To test program effects on bystander behavior, we will estimate GLMMs predicting bystander behaviors at follow-up, adjusting for baseline bystander behavior as well as any relevant covariates identified in preliminary analyses. GLMMs will include random components for bar-level intercepts. To address mediation of program effects via TPB constructs, we will estimate prospective MSEMs in which the effect of study arm on bystander behavior is mediated through its effects on TPB constructs. Point estimates of indirect effects will be computed using a product-of-coefficients approach [21]. As MPlus does not produce bootstrap standard errors for indirect effects in multilevel SEMs, Bayesian credible intervals will used for inference. To address potential moderation of program effects by participant characteristics (gender identity, job position, education, personal sexual assault experiences, prior education in sexual assault prevention) and bar characteristics (policies, physical environment), we will extend above GLMMs by including Study Arm x Characteristic interaction terms. Each significant interaction will be probed to characterize the pattern of differential program effects across categories or levels of a background characteristic [22].

Bar-level Analyses

Within a generalized linear modeling framework, a series of ANCOVAs will be conducted to examine the effect of intervention condition on changes in physical environment characteristics and risk management safety policies. Outcome scores at 3-month follow-up will be predicted from study arm, adjusting for baseline scores and relevant bar-level covariates. The Sidak procedure will be used to control study-wise Type 1 error inflation.

Community-level Analyses

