Violent crime datasets will be obtained from relevant municipal police departments via public records requests for years prior to and during the study. Maps will be generated using ArcGIS ArcMap. Violent crimes of interest will be mapped using the "Esri World Geocoder" under the "Geocode Addresses" tool and then shapefile layers will be created.

Next, spatial information of the liquor licenses for the relevant bars will be obtained from the Arizona Department of Liquor Licenses and Control (DLLC) website. Only "on-premises" liquor license addresses will be queried and mapped. Shapefile layers of bar locations will be created and added to the maps. Utilizing the "Kernel Density" tool within the "Spatial Analyst

Toolbox" via ArcMaps, bar location density will be mapped against the crime points. The results will illustrate the amount of violent crime in a specific location in relation to the density of bars for that exact location. Analyses will compare the frequency of violent crime-related police dispatches to study catchment areas before and after receiving *Safer Bars* training.

Power Analysis

The sample size of 564 individual bar staff (approximately 56 bars [28 bars in each study arm] x average of 10 participants per bar) affords power of .80 to detect small-to-moderate standardized between-group differences (i.e., intervention effects) on individual-level outcomes ranging from d = 0.28 to 0.45, depending on an assumed intraclass correlation (ICC) of .10 for outcome scores, assumed correlations between baseline and follow-up scores ranging from r = .10 to .50, and assumed ICCs for pre-post change scores ranging from .05 to .10. Adjusting for bar-level clustering, the proposed sample should afford power of .80 to detect indirect effects and small-to-moderate constituent direct effects (ds= 0.35-0.45 for X to M, r2s = .04-.09 for M to Y), assuming a 10% attrition rate. For bar-level outcomes, the proposed sample size affords power to detect large effects (ds = 0.66-0.76, for pre-post correlations of r = .10-.50).

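### The bar-level detectable effects (d = 0.66-0.76) match a single unadjusted two-sided .05 test, although the plan applies Sidak control to these outcomes; alpha and number of tests are not stated

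*Combined protocol and SAP*

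**What the plan says.** The SAP's Bar-level Analyses section states that "a series of ANCOVAs will be conducted to examine the effect of intervention condition on changes in physical environment characteristics and risk management safety policies". The model is an ANCOVA: "Outcome scores at 3-month follow-up will be predicted from study arm, adjusting for baseline scores and relevant bar-level covariates". The section closes with "The Sidak procedure will be used to control study-wise Type 1 error inflation". It gives neither the number of tests nor the family-wise alpha, and does not say whether Sidak is single-step or step-down.

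The Power Analysis section assumes "approximately 56 bars [28 bars in each study arm"]. For individual-level outcomes the sample "affords power of .80 to detect small-to-moderate standardized between-group differences", and the next sentence, on indirect effects, also uses .80. The bar-level sentence comes last: "For bar-level outcomes, the proposed sample size affords power to detect large effects (ds = 0.66-0.76, for pre-post correlations of r = .10-.50"). It names no power level, alpha, sidedness, number of tests or loss of bars, and does not mention Sidak.

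**The concern.** A detectable effect describes a particular test at a particular alpha. The bar-level section commits to more than one test, since it plans a series over two named domains, and to Sidak control, so each test is held to a stricter threshold than .05. If the stated range was computed at .05 for a single test, it describes a more powerful test than the planned one.

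This matters most when a bar-level result is null. The range is the only statement in the SAP of what 56 bars can show on the physical environment and safety policies. A reader would assume a 20% chance of missing an effect of the stated size. Under the planned adjustment that chance may be nearer 29%, and higher with more tests.

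**Working it through.** **Inputs**

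- Bars per arm n = 28 and pre-post correlation r = .10 to .50 (Power Analysis).
- ANCOVA on the 3-month score adjusted for baseline (Bar-level Analyses).
- Power .80: inferred from the preceding sentences of the Power Analysis.
- Two-sided testing at overall .05: assumed, not stated.
- No loss of bars: assumed. The 10% attrition rate appears only in the indirect-effects sentence.

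**Formula**

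The standard error of the adjusted difference in SD units is sqrt((2/n)(1 − r²)), with df = 2n − 3 = 53. The detectable effect is d = λ · sqrt(2/28) · sqrt(1 − r²) = λ · 0.2673 · sqrt(1 − r²). Here λ is the noncentrality that gives .80 power in the noncentral t distribution. The factor sqrt(1 − r²) is 0.8660 at r = .50 and 0.9950 at r = .10.

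**Step 1: reproduce the stated range (one test, two-sided .05)**

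The critical t is 2.006 and λ = 2.854.

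- r = .50: 2.854 × 0.2673 × 0.8660 = 0.660
- r = .10: 2.854 × 0.2673 × 0.9950 = 0.759

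Both ends match 0.66 and 0.76. Power at the stated values is .799 and .801.

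Three variants do not match: one-sided .05 without adjustment (0.58-0.67), change scores (0.75-1.01) and 10% loss of bars (0.70-0.80).

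**Step 2: apply single-step Sidak**

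For k tests, alpha_k = 1 − .95^(1/k). With k = 2, alpha is .02532, the critical t is 2.302 and λ = 3.153.

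- r = .50: 3.153 × 0.2673 × 0.8660 = 0.730
- r = .10: 3.153 × 0.2673 × 0.9950 = 0.838

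The ratio to the unadjusted values is 3.153 / 2.854 = 1.105, so the detectable effect is about 10% larger. The number of tests is not given, so the table shows a range of k:

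| k (two-sided) | alpha per test | detectable d, r = .50 / .10 | power at 0.66 / 0.76 |
|---|---|---|---|
| 1 | .0500 | 0.660 / 0.759 | .799 / .801 |
| 2 | .0253 | 0.730 / 0.838 | .708 / .710 |
| 3 | .0170 | 0.768 / 0.883 | .651 / .653 |
| 4 | .0127 | 0.795 / 0.913 | .609 / .612 |
| 5 | .0102 | 0.815 / 0.936 | .577 / .579 |

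**Step 3: step-down Sidak, two tests**

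The smaller p-value is compared with .02532 and, if it passes, the larger with .05. Power is per outcome, from 400,000 simulated draws of correlated noncentral t statistics.

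| True effects | detectable d, r = .50 / .10 | power at 0.66 / 0.76 |
|---|---|---|
| both, outcome correlation 0 | 0.681 / 0.782 | .772 / .774 |
| both, outcome correlation .3 | 0.685 / 0.787 | .767 / .769 |
| both, outcome correlation .6 | 0.690 / 0.793 | .760 / .762 |
| one only, independent outcomes | 0.728 / 0.837 | .710 / .712 |

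Full ANCOVA simulations with a random baseline (40,000 replicates per setting, outcome correlations 0 to .6) gave similar results: power .788-.795 unadjusted, .696-.704 single-step and .753-.768 step-down.

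**Step 4: how much covariates would have to add**

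For two single-step tests to keep the stated d at .80 power, sqrt(1 − R²) must equal d / (3.153 × 0.2673).

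- d = 0.66: 0.783, so R² = .387 and R = .62. Baseline alone gives r² = .25; the extra is .137.
- d = 0.76: 0.902, so R² = .187 and R = .43. Baseline alone gives r² = .01; the extra is .177.

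This ignores the degrees of freedom that added covariates would use.

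**Step 5: adjusted readings that also fit the stated range**

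Each needs exactly two tests.

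- One-sided Sidak at overall .05: λ = 2.848, d = 0.659 / 0.757. With three tests it becomes 0.701 / 0.805 and no longer fits.
- Two-sided Sidak at overall .10 (alpha per test 1 − .90^(1/2) = .0513): λ = 2.842, d = 0.658 / 0.756.

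**The case against.** The strongest reply is that nothing here is contradictory, only under-specified. The power sentence never claims to be adjusted for multiplicity, and a per-test detectable effect can stand beside a multiplicity-controlled analysis without either being false. The match also does not prove which calculation was done: power, sidedness and alpha all had to be supplied, and the two readings in step 5 carry an adjustment and still round to 0.66-0.76.

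Much of this stands. No arithmetic error is proven, and the figures alone cannot separate adjusted from unadjusted. But the adjusted readings need one-sided testing or an overall alpha of .10, plus exactly two tests, and none of these is stated. On the conventional two-sided .05 reading no family of two or more tests reproduces the range.

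The second reply concerns size. The count of two is inferred from the two named domains, step-down Sidak costs only 3 to 4 points of power when both effects are real, and the planned bar-level covariates could close the gap. This is fair, and for that reason the two-test figures illustrate the size of the gap and do not replace the plan's own numbers. However, two is the smallest count a series allows, and more tests widen the gap. The power statement credits only the pre-post correlation, and the covariates are not named.

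Finally, the description of the effects as large survives adjustment, and Type I error control is unaffected. Both are true, and they keep the point minor.

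**Conclusion.** The concern holds, as a minor point. The stated range equals that of one unadjusted two-sided .05 test with all 56 bars retained and .80 power. The plan, however, tests several bar-level outcomes with Sidak control, and a reader cannot tell from the SAP which test the range describes.

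With two two-sided tests, overall .05, 28 bars per arm and baseline adjustment only, the chance of missing an effect of the stated size on a given outcome is about 29% with single-step Sidak. With step-down Sidak it is about 23-24% if both effects are of that size and about 29% if only one is real. The inferred target is 20%.

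The match of the figures and the absence of alpha and number of tests are certain. That the adjustment was left out is the conventional reading, not a proven fact.

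**What to change.** Restate the bar-level detectable effects at the Sidak-adjusted alpha for the actual number of bar-level tests. For two two-sided single-step tests without further covariates this would be about d = 0.73-0.84. Alongside the range, state:

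- the overall alpha, sidedness and power;
- the number of bar-level tests;
- whether Sidak is single-step or step-down;
- any multiple correlation from covariates that the figure relies on;
- the number of bars assumed to contribute at 3 months.

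If the range was meant as unadjusted and per test, or as one-sided with Sidak for two tests, saying so is enough.

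The cost is one recomputation and one or two sentences. Sample size, design and tests stay as they are. If the range is restated on the two-sided basis, the published detectable effect becomes slightly less favourable.
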